7.2.4.8 Neurological examinations

In the morning following each PSG night (V2, V3, V4, V5, V6 and V7), a set of examinations must be performed approximately 1 hour after lights on [see Section 7.2]. The neurological examinations will be done by the investigator, a delegated physician, a specialist nurse or a nurse practitioner, trained according to local requirements and local clinical practice. The following examinations will be performed to detect a possible next-day residual effect :

- Gait
- Tandem walking
- Romberg test.

The set of examinations will be repeated approximately every 30 minutes until it is safe for the subject to leave the center [see Section 7.2]. The time when it is considered safe for the subject to leave the center will be recorded in the eCRF.

7.2.4.9 ECG assessment

A standard 12-lead ECG is to be performed, at V1 and in the second morning of V2, V3, V4, V5, V6 and V7.

12-lead ECG will be recorded at rest with the subject in the supine position for a 5-minute period. Data records will be sent to the evaluation center for central reading.

Details will be provided in the 12-lead ECG laboratory manual.

The following parameters will be evaluated: PQ or PR (ms), QRS (ms), QT (ms), heart rate [HR] (bpm), and rhythm. QT_C (ms) will be calculated according to

- Bazett's formula: $QT_C = QT / (RR)^{1/2}$
and
- Fridericia's formula: $QT_C = QT / (RR)^{1/3}$, where $RR = 60 / HR$

If the central review of the ECG detects a prolonged QTc interval greater than 450 ms for a subject at screening (V1, V2), ECG must be repeated (at least 30 minutes after first ECG on the same day). If the central review confirms that the repeated ECG shows a QTc interval greater than 450 ms, the subject cannot be enrolled into the study.

Clinically relevant findings made after randomization that meet the definition of an AE must be recorded in the eCRF.

ECG data collected by the CRO will be electronically transferred to Actelion.

7.2.5 Laboratory assessments

7.2.5.1 Type of laboratory

A central laboratory (see central laboratory manual for contact details) will be used for all protocol-mandated laboratory tests, including re-tests due to laboratory abnormalities and laboratory tests performed at unscheduled visits.

Exceptional circumstances that will require recording of local laboratory results of the parameters described in Section 7.2.5.2 (with corresponding normal ranges), include hospitalization of the subject due to a medical emergency, and missing central laboratory results from a scheduled or unscheduled visit.

If one central laboratory sample is lost or cannot be analyzed for whatever reason, the investigator will collect an additional sample as soon as possible for repeat analysis, unless a local laboratory sample was collected within the same time-window and these test results are available.

Central laboratory reports will be sent to the investigator. In case of specific (pre-defined) laboratory abnormalities, the central laboratory will alert Actelion and the concerned site. Alert flags that will trigger such notifications are displayed in [Appendix 1](#).

All laboratory reports must be reviewed, signed and dated by the investigator or delegate within 10 working days of receipt and filed with the source documentation. The

investigator/delegate must indicate on the laboratory report whether abnormal values are considered clinically relevant or not. Clinically relevant laboratory findings that are known at the time of signature of informed consent must be recorded on the medical history page of the eCRF. Any clinically relevant laboratory abnormalities detected after signature of informed consent must be reported as an AE or SAE as appropriate [see Section 9] and must be followed until the value returns to within the normal range or is stable, or until the change is no longer clinically relevant.

Details about the collection, sampling, storage, shipment procedures, and reporting of results and abnormal findings can be found in the laboratory manual.

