1.4.2 Safety and risk-minimization measures taken in the present study

Next-day sleepiness may potentially occur with ACT-541468. On each of the mornings following drug administration in sleep centers, the subjects will undergo neurological examinations based on the evaluation of gait, the Tandem Walking Test and the Romberg Test. Based on the results of the neurological examination, the investigator will discuss with the subjects and decide whether it is safe for the subject to leave the study centers.

As required by current guidelines, the Columbia Suicide Severity Rating Scale (C-SSRS[®]) will be completed by the subjects on each morning after the polysomnography (PSG) nights at visit (V) 2 to V7 to assess suicidality prior to randomization and during the double-blind treatment phase.

Liver variables and other laboratory variables will be monitored in the study at each study visit.

Due to lack of data about interaction of ACT-541468 with food, the study treatment will be administered at least 2 hours after a meal.

Elderly subjects enrolled in this study will receive the study treatment only at the sleep centers and will not be discharged from the sleep centers with the study treatment.

Two committees will be set up for the study:

- An Independent Safety Board (ISB) will review and adjudicate in a blinded manner all AEs of special interest, i.e., narcolepsy-like events (e.g., excessive daytime sleepiness, cataplexy), complex sleep behavior events and suicidal thoughts and/or behaviors.
- An Independent Data Monitoring Committee (IDMC) will monitor safety and efficacy data in an unblinded manner and make appropriate recommendations to ensure safety of the subjects.

It is the investigator's responsibility to monitor the risk-benefit ratio of study treatment administration, as well as the degree of distress caused by study procedures on an individual subject level, and to discontinue study treatment or the study if, on balance, he/she believes that continuation would be detrimental to the subjects' well-being.

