3.1.1.2 Double-blind treatment phase

The double-blind **treatment phase** starts with the first dose of study treatment in the first evening of the Randomization visit (V3) and ends in the second morning of V7. It consists of five **treatment periods**, each consisting of two consecutive PSG nights on the assigned study treatment followed by a 5- to 12-day washout.

The **End of Treatment (EOT)** is reached in the second morning of V7, after the last dose of double-blind treatment and after all morning assessments have been performed.

The **safety Follow-up phase** starts after the EOT and lasts at least 30 days (i.e., until the second follow-up telephone call). A first telephone call is done 5 days (+ 7 days) after EOT to collect TEAEs from the last study treatment dose.

[figure not shown]
The **End of Study (EOS)** for a single subject is defined as the date of the 30-day follow-up telephone call. If a subject withdraws consent and does not wish to participate in the study any longer, EOS is the date of consent withdrawal for this subject. If a subject is declared lost to follow-up [see also Section 8.2], EOS is the date of last successful contact for this subject.

Unscheduled visits are allowed to take place anytime during the study, in which case study-related information will be collected.

The visit schedule and protocol-mandated procedures will be performed according to the table of assessments [Table 3] and are described in Section 7.

The overall study design is depicted in [Figure 1].

Figure 1 Study design

V = visit; — polysomnographic (PSG) nights; D = dose; P = placebo.

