5.1.9 Premature discontinuation of double-blind study treatment

The decision to prematurely discontinue study treatment may be made by the subject, the investigator or Actelion. The main reason and whether discontinuation of study treatment is the decision of the subject (e.g., tolerability- or efficacy-related), the investigator (e.g., due to pre-specified study treatment discontinuation criteria, an AE or lack of efficacy), or Actelion (e.g., study terminated) must be documented in the eCRF and in the subject medical charts.

A subject has the right to prematurely discontinue study treatment at any time, without any justification, by withdrawal from study treatment only or by withdrawal from any further participation in the study (i.e., premature withdrawal from the study [see Section 8.2]). Although a subject is not obliged to give his/her reason for prematurely withdrawing from the treatment or the study, it is recommended that the investigator makes a reasonable effort to ascertain the reason(s) while fully respecting the subject's rights.

The investigator must discontinue study treatment for a given subject if he/she believes that continued administration would be contrary to the best interests of the subject.

A subject must be discontinued from the study in case of:

- $ALT \geq 3 \times$ the ULN and total Bilirubin $> 2 \times$ the ULN on the morning laboratory test following the second drug intake of each treatment period,

or

- ALT and / or $AST > 5 \times$ the ULN on the morning laboratory test following the second drug intake of each treatment period.

A subject who prematurely discontinues study treatment is NOT considered as withdrawn from the study and will be followed up until EOS provided that the subject consents to this limited participation in the study.

Subjects who prematurely discontinue treatment during a treatment period at the center will undergo the morning assessments after the last study drug intake. All subjects who prematurely discontinue study treatment will be asked to agree to be called for the safety

follow-up (one telephone call 5 days [+ 7 days] after the last intake of study treatment, and a second telephone call at least 30 days after the last intake of study treatment).

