7 VISIT SCHEDULE AND STUDY ASSESSMENTS

7.1 Study visits

The study visits are listed in [Table 3](#). For all double-blind treatment phase visits (V3 to V7), the subjects must be seen between 5 and 12 days after the previous visit. Two follow-up safety telephone calls must be performed: one telephone call 5 days (+ 7 days) after the last intake of study treatment, and a second telephone call at least 30 days (+ 7 days) after the last intake of study treatment.

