7.2 Study assessments

The mandatory study assessments are listed in [Table 3](#).

All study assessments are performed by qualified study staff (medical, nursing, or specialist technical staff) and are recorded in the eCRF, unless otherwise specified. Study assessments performed during unscheduled visits will also be recorded in the eCRF. The following order of assessments is recommended:

- In the evening before PSG night:
 - Physical examination (first evening)
 - Vital signs and body temperature (first evening)
 - Drug and alcohol test
 - Hematology and blood chemistry (first evening at V3, V4, V5, V6 and V7)
 - Evening questionnaire in sleep diary, including VAS (second evening)
 - Recording of concomitant medications
 - AEs and SAEs
 - Study drug intake 30 minutes (\pm 5 minutes) before lights off
- In the morning after PSG night, after completion of normal morning routine (e.g., using the bathroom, eating breakfast):
 - Physical examination (second morning at V7)
 - Vital signs and body temperature
 - DSST[®]
 - SDS[®]
 - KSS
 - C-SSRS[®]
 - Morning questionnaire in sleep diary (including VAS)
 - Recording of concomitant medications
 - AEs and SAEs
 - Neurological examination*

- Hematology and blood chemistry (second morning)
- PK sampling* (second morning at V3, V4, V5, V6 and V7)
- 12-lead ECG (second morning)

*The neurological examination must be performed approximately 1 hour after lights on and repeated approximately every 30 minutes until it is safe for the subject to leave the center. In the event of excessive sleepiness according to investigator opinion one hour after lights on in the morning after the first PSG night, it is recommended to draw a PK sample at this time.

The following assessments will be analyzed by an external provider (results will be transferred to the Actelion database and to the investigators):

- Lab parameters
- ECG parameters
- PSG recordings
- Questionnaires completed using a hand-held device (listed below)

If the principal investigator (PI) delegates any study procedure/assessment for a subject to an external facility, he/she must inform Actelion to whom these tasks are delegated. The set-up and oversight will be agreed upon with Actelion. The supervision of any external facilities remains the responsibility of the PI.

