Parameters	Sex	Conventional US Reporting of Reference Ranges									SI Reporting Reference Ranges								
		Units	Ref Range Low	Ref Range High	Flag L at	Flag H at	Flag LL at	Flag HH at	Call Alert Low at	Call Alert High at	Units	Ref Range Low	Ref Range High	Flag L at	Flag H at	Flag LL at	Flag HH at	Call Alert Low at	Call Alert High at
Clinical Chemistry																			
Alanine aminotransferase	M	U/L	0	44	NA	45	NA	132	NA	NA	U/L	0	44	NA	45	NA	132	NA	NA
Alanine aminotransferase	F	U/L	0	33	NA	34	NA	99	NA	NA	U/L	0	33	NA	34	NA	99	NA	NA
Albumin	M/F	g/dL	3.5	5.2	3.4	5.3	2.0	7.1	2.0	7.1	g/L	35	52	34	53	20	71	20	71
Alkaline phosphatase	M	U/L	53	129	52	130	NA	440	NA	NA	U/L	53	129	52	130	NA	440	NA	NA
Alkaline phosphatase	F	U/L	42	98	41	99	NA	440	NA	NA	U/L	42	98	41	99	NA	440	NA	NA
Aspartate aminotransferase	M	U/L	14	39	13	40	NA	117	NA	NA	U/L	14	39	13	40	NA	117	NA	NA
Aspartate aminotransferase	F	U/L	14	34	13	35	NA	102	NA	NA	U/L	14	34	13	35	NA	102	NA	NA
Bilirubin, direct	M/F	mg/dL	0.0	0.3	NA	0.4	NA	3.0	NA	NA	umol/L	0.0	5.1	NA	5.2	NA	51.3	NA	NA
Bilirubin, total	M/F	mg/dL	0.3	1.2	0.2	1.3	NA	3.3	NA	NA	umol/L	5.1	20.5	5.0	20.6	NA	56.5	NA	NA
Blood Urea Nitrogen (BUN)	M/F	mg/dL	9	23	8	24	NA	70	NA	NA	mmol/L	3.2	8.2	3.1	8.3	NA	25.0	NA	NA
Calcium	M/F	mg/dL	8.6	10.2	8.5	10.3	6.8	12.0	6.8	14.0	mmol/L	2.15	2.55	2.14	2.56	1.70	3.00	1.70	3.50
Chloride	M/F	mmol/L	99	109	98	110	74	131	NA	NA	mmol/L	99	109	98	110	74	131	NA	NA
Cholesterol, total	M/F	mg/dL	0	199	NA	200	NA	602	NA	NA	mmol/L	0.0	5.2	NA	5.3	NA	15.6	NA	NA
Creatinine	M	mg/dL	0.70	1.30	0.69	1.31	NA	3.00	NA	NA	umol/L	62	115	61	116	NA	265	NA	NA
Creatinine	F	mg/dL	0.50	1.10	0.49	1.11	NA	3.00	NA	NA	umol/L	44	97	43	98	NA	265	NA	NA
Creatine kinase	M	U/L	32	294	31	295	NA	525	NA	NA	U/L	32	294	31	295	NA	525	NA	NA
Creatine kinase	F	U/L	33	211	32	212	NA	525	NA	NA	U/L	33	211	32	212	NA	525	NA	NA
GGT	M	U/L	0	54	NA	55	NA	162	NA	NA	U/L	0	54	NA	55	NA	162	NA	NA
GGT	F	U/L	0	37	NA	38	NA	111	NA	NA	U/L	0	37	NA	38	NA	111	NA	NA
Glucose, Random	M/F	mg/dL	60	140	59	141	40	360	NA	NA	mmol/L	3.3	7.8	3.2	7.9	2.2	20.0	NA	NA
Potassium (K)	M/F	mmol/L	3.5	5.1	3.4	5.2	2.5	6.5	2.5	6.5	mmol/L	3.5	5.1	3.4	5.2	2.5	6.5	2.5	6.5
Sodium (Na)	M/F	mmol/L	136	145	135	146	119	161	NA	NA	mmol/L	136	145	135	146	119	161	NA	NA

Triglycerides	M/F	mg/dL	0	149	NA	150	NA	NA	NA	NA	mmol/L	0.00	1.68	NA	1.69	NA	NA	NA	NA
Uric acid	F	mg/dL	2.3	6.6	2.2	6.7	NA	13.1	NA	NA	umol/L	137	393	136	394	NA	780	NA	NA
TSH	M/F	μIU/mL	0.35	5.50	0.34	5.51	NA	NA	NA	NA	mIU/L	0.35	5.50	0.34	5.51	NA	NA	NA	NA

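### The 10-working-day review limit for laboratory reports outlasts the 5 to 12 days before the next dose, so no stated deadline makes the mandatory liver stopping rule work in time

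*Protocol*

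**What the plan says.** Protocol section 5.1.9 sets two liver criteria: ALT at or above 3 x ULN together with total bilirubin above 2 x ULN, or ALT and/or AST above 5 x ULN. The instruction is mandatory ("A subject must be discontinued from the study in case of"), and both criteria are read "on the morning laboratory test following the second drug intake of each treatment period".

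Section 7.2.5.1 sends all protocol-mandated samples to a central laboratory and sets one time limit for the site: "All laboratory reports must be reviewed, signed and dated by the investigator or delegate within 10 working days of receipt". The same section says that the central laboratory will alert the sponsor and the site to certain pre-defined abnormalities, and points to the flags in Appendix 1. It leaves the details of reporting to a laboratory manual.

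Section 7.1 fixes the interval to the next period: "the subjects must be seen between 5 and 12 days after the previous visit". Section 3.1.1.2 agrees, with periods "each consisting of two consecutive PSG nights on the assigned study treatment followed by a 5- to 12-day washout".

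Section 1.4.2 lists liver monitoring among the risk-minimization measures: "Liver variables and other laboratory variables will be monitored in the study at each study visit".

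**The concern.** A stopping rule applied after every period can prevent further exposure only if each result is known before the next period starts. The one deadline that the protocol gives for reading the result runs longer than the longest permitted gap between periods.

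Elsewhere the protocol does set such links. Section 7.2.5.2 makes dosing conditional on negative drug and alcohol tests. Section 7.2.3.1 gives the scoring centre 3 business days to return the PSG eligibility assessment. Nothing comparable ties the liver result to V4, V5, V6 or V7.

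These are the only numeric criteria for discontinuing a subject in the protocol. A subject over a limit after one period could receive two more nights of study drug, in some sequences at a higher dose, before anyone was obliged to look at the report. Section 1.3.2 says that the highest evening dose previously given to healthy elderly subjects was 25 mg; this study goes to 50 mg.

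**Working it through.** **1. The plan's own timetable.** Section 3.1.2 gives a double-blind phase of 30 to 58 days. Five periods of 2 days and four washouts of 5 to 12 days give 5 x 2 + 4 x 5 = 30 and 5 x 2 + 4 x 12 = 58. The figure reproduces, so the gap between periods is 5 to 12 days.

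**2. The review limit in calendar days.** Ten working days are two calendar weeks, or 14 days, against a gap of 5 to 12. For an exact count, take each of the 7 possible sampling weekdays and each of the 8 permitted gaps (5 to 12 days): 7 x 8 = 56 schedules. The documents give no turnaround from sampling to receipt, so 0 to 3 days is assumed. Public holidays are ignored; they would lengthen the limit.

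| Turnaround (days) | Receipt day counted? | Deadline, days after sampling | Next dose strictly before deadline |
|---|---|---|---|
| 0 | no | 12–14 | 55/56 |
| 1 | no | 13–15 | 56/56 |
| 2 | no | 14–16 | 56/56 |
| 3 | no | 15–17 | 56/56 |
| 0 | yes | 11–13 | 53/56 |
| 1 | yes | 12–14 | 55/56 |
| 2 | yes | 13–15 | 56/56 |
| 3 | yes | 14–16 | 56/56 |

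The few exceptions need a turnaround of 0 or 1 day and a gap of 11 or 12 days. A longer turnaround removes them.

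**3. How often the situation arises.** Each subject has 4 moves from one period to the next, so 50 subjects have at most 50 x 4 = 200. In Table 1 of the protocol, 5 of the 20 moves go from an active dose to a higher active dose: one each in sequences 1, 3 and 5, two in sequence 4, none in sequence 2. At 10 subjects per sequence that is 5 x 10 = 50 of 200. These are counts of opportunities before dropout, not of subjects expected to meet the rule.

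**4. Does the laboratory alert cover the rule?** HH flags in Appendix 1, divided by the upper reference limit:

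- ALT: 132/44 = 3.0 (men), 99/33 = 3.0 (women)
- AST: 117/39 = 3.0 (men), 102/34 = 3.0 (women)
- "Bilirubin, total": 3.3/1.2 = 2.75, against 2 x 1.2 = 2.4 mg/dL in the rule

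The first criterion needs ALT at or above 3 x ULN; the second needs ALT or AST above 5 x ULN. Every subject meeting either one therefore reaches an ALT or AST HH flag. The Call Alert columns, however, read NA for ALT, AST and both bilirubins, although they hold values for hematocrit, INR, albumin, calcium and potassium. Section 7.2.5.1 does not say which columns cause a notification. It states no time limit for the alert and no step that links it to the next visit.

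**The case against.** The strongest reply is that the 10 working days are an outer limit for reading, signing and filing all reports, and were never meant as the way to detect a liver signal. Detection is the job of the central-laboratory alert, described in the paragraph just before the limit, and section 9.3 adds continuous safety review by the sponsor. If HH flags trigger the alert, no case that meets the rule goes unflagged. This stands as real mitigation. It does not settle the matter, because the trigger column is ambiguous, no alert timing is given, and the sponsor's review is not timed to the next dose. The laboratory manual may supply these details, but it was not available here.

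Three stronger readings are tempting and not supported:

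- A reader might infer that the protocol permits re-dosing a subject over the limits. It does not. Section 5.1.9 is unconditional, so such a dose would conflict with it. What is missing is a deadline that makes the rule workable.
- A reader might infer that total bilirubin between 2.0 and 2.75 x ULN slips through. It counts only together with ALT at or above 3 x ULN, which has its own HH flag. If only Call Alert notifies, no liver value does, and the band again makes no difference.
- Blood is also taken before dosing ("Hematology and blood chemistry (first evening at V3, V4, V5, V6 and V7"), and 5.1.9 does not use that sample. A reader might call this a contradiction of 1.4.2. Monitoring at each visit does not make every sample a stopping trigger; which sample triggers is a design choice.

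Subjects with ALT or AST above 2 x ULN at V1 or V2 are excluded, which also makes events less likely.

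**Conclusion.** The inconsistency is real, and it is one of timing. In nearly all permitted schedules (53 to 56 of 56, depending on assumed turnaround and on how the receipt day is counted) a site can meet the review deadline and give the next period's dose before anyone is required to have read the result on which the mandatory rule depends. The laboratory alert may close much of the gap, but the protocol as written does not establish that it does.

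The number of subjects affected is unknown and probably low; the documents give no rate at which the limits would be met. The conclusion rests on the assumed turnaround of 0 to 3 days and on the protocol text alone. A laboratory manual with a firm alert time for HH liver values would reduce the point to a missing cross-reference.

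**What to change.** Reconcile sections 5.1.9, 7.1, 7.2.5.1 and Appendix 1 on two matters:

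1. Make the deadline for knowing the second-morning liver result consistent with the 5 to 12 days before the next period.
2. State which Appendix 1 flags notify the site and sponsor for liver parameters, and how quickly. If the laboratory manual already says so, cite it in 7.2.5.1.

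The sponsor chooses the mechanism. No threshold, dosing rule or triggering sample is proposed here.

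The cost is a few sentences and possibly one alert setting at the central laboratory, with no extra samples. Sites would have to read one report per period sooner. An occasional visit might need rescheduling, and a visit already at day 12 has no room left in the window, so the text should anticipate that case.

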7.2.5.2 Laboratory tests

Hematology

- Hemoglobin (g/L)
- Hematocrit (L/L)
- Erythrocytes ($10^9/L$)
- Reticulocytes (%)
- Leukocytes with differential counts ($10^9/L$)
- Platelets ($10^9/L$)
- Prothrombin time and international normalized ratio

Clinical chemistry

- ALT (U/L)
- AST (U/L)
- Alkaline phosphatase (U/L)
- Creatine kinase (mcg/L)
- Total and direct bilirubin ($\mu\text{mol/L}$)
- Gamma-glutamyl transferase (U/L)
- Creatinine ($\mu\text{mol/L}$)
- Blood urea nitrogen (mmol/L)
- Uric acid ($\mu\text{mol/L}$)
- Glucose (mmol/L)
- Cholesterol, triglycerides (mmol/L)
- Sodium, potassium, chloride, calcium (mmol/L)
- Albumin (g/L)
- Thyroid hormones (triiodothyronine, thyroxine), and thyroid-stimulating hormone

Other tests

The urine drug screening kits (testing for presence of benzodiazepines, barbiturates, cannabinoids, opiates, amphetamines, or cocaine) and the breathalyzer for alcohol detection in the exhaled breath will be provided by the central lab.

Study drug is administered as described in Section 5 only if the results of these other tests are negative.

